6.0 Data and Safety Monitoring

The procedures administered for this research will be done in a manner that is consistent with clinical care. Therefore, an internal monitoring plan that includes the PI and all co-investigators will be implemented. Study team members will meet quarterly to discuss study progress including enrollment, data acquisition, and adverse events. In the event any unanticipated problems occur during the course of this research, they will be reported to the Institutional Review Board (IRB) in accordance with posted policies.

7.0 Privacy and Confidentiality

Information about study subjects will be kept confidential and managed according to the requirements of the Health Insurance Portability and Accountability Act of 1996 (HIPAA). Subjects will be assigned a unique study number upon enrollment that will be used to label their research data in lieu of directly identifiable information. All subject data collected during participation in the study will be kept in a locked file cabinet within a Department of Radiology office or a password-protected database that uses departmental servers and will only be accessible to study team members. Coded data and images will be shared with [name] at New York University. The Department of Radiology Radius team will serve as the honest broker and will code and share data with NYU. After the study is completed, all data will be de-identified for the purposes of research presentations/publications. The study MRI and US examinations will be archived on the standard clinical PACS system which is password protected behind the UWHC firewall. The study data and records will be maintained for up to 5 years after the conclusion of the study, at which point the PI will destroy the key to the coded identifiers, thus permanently anonymizing the data.

8.0 Statistical Considerations

A similar study involving patients with PT estimated the pooled standard deviation (SD) of the changes in VISA-P score over time to be between 15 and 19 and the minimal detectable

	N per group	Change in DN	Change in SH	Change in PRP	Pooled SD	Power (%)
20	5.5	5.5	22	10	99.9	
20	5.5	5.5	22	15	94.8	
20	5.5	5.5	22	20	75.1	
20	5.5	5.5	16.5	10	94.8	
20	5.5	5.5	16.5	20	64.2	
20	5.5	5.5	11	5	94.8	

Table 2

change in score

to be 11.1 (41). Since our subjects will have already completed physical therapy without improvement, we hypothesize that the DN and SH groups will marginally improve and that the PRP group will significantly improve on the order of 3 times the improvement of the other groups over the 1 year follow-up period. With 20 subjects, table 2 shows the expected power of our study based on hypothesized changes over time and the pooled SD of the changes in VISA-P scores. To allow for 10% drop out, we will recruit 22 subjects per group. Based on the estimated SD for

the changes in the VISA-P scores reported in the previous study, we are conservatively inflating our pooled SD estimate.

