3.0 STUDY AIMS/STUDY OBJECTIVES

The purpose of this research is to find an effective treatment for PT that addresses the underlying pathophysiology of tissue degeneration.

3.1 Specific aims include:

- 3.1.1 To evaluate the efficacy of PRP by reporting improved pain- and function-dependent, PT-specific Victorian Institute of Sport Assessment Patella (VISA-P) quality of life scores, Tegner activity level scores, and knee strength at baseline, 16, 32, and 52 weeks post-treatment.
- 3.1.2 To demonstrate treatment-related changes in pathologic imaging features of PT using conventional MRI (thickness and T2 signal intensity) and US (thickness, echogenicity, and hyperemia).
- 3.1.3 To investigate the relationship between changes in novel quantitative MRI (single-component and bicomponent ultra-short echo-time T2* (UTE-T2*)) and US (shear wave speed (SWS), a proxy for elasticity) parameters of PT and clinical and biomechanical improvement following treatment.

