4.0 SELECTION OF PATIENTS

- 4.1 Study Population: This research will enroll 10 healthy normal adults and 66 adults diagnosed with chronic patellar tendonitis.
- 4.2 Eligibility criteria (healthy/normal)
 - 4.2.1 Age between 18 and 39 years
 - 4.2.2
- 4.3 Eligibility criteria (Subjects diagnosed with chronic patellar tendonitis)
 - 4.3.1 Inclusion criteria
 - 4.3.1.1 Age between 18 and 39 years
 - 4.3.1.2 Chronic (>3 months) PT
 - 4.3.1.3 Clinical examination consistent with PT
 - 4.3.1.4 MRI or US confirmation of PT
 - 4.3.1.5 Pain score of 3 or greater on a 10-point VAS
 - 4.3.1.6 Self-report failure of supervised physical therapy

- 4.3.1.7 Self-report failure of at least 2 of the most common treatment options for PT (e.g. NSAIDs, relative rest, ice and bracing).
- 4.3.2 Exclusion criteria (All subjects)
 - 4.3.2.1 Inability to comply with study follow-up requirements
 - 4.3.2.2 History of bleeding disorders or other hematologic conditions
 - 4.3.2.3 Knee pain from other possible etiologies (e.g., degenerative joint disease, meniscal tear, ligament injury or reconstruction)
 - 4.3.2.4 Full or partial patellar tendon tear
 - 4.3.2.5 Current use of anticoagulation or immunosuppressive therapy
 - 4.3.2.6 Prior knee trauma requiring medical attention or surgery
 - 4.3.2.7 Self-reported pregnancy
 - 4.3.2.8 Worker's compensation injury
 - 4.3.2.9 Daily opioid use for pain
 - 4.3.2.10 Contraindication to MRI.
 - 4.3.2.11 Systemic diseases such as Diabetes and connective tissue diseases.
 - 4.3.2.12 Prior PRP or DN procedure.
 - 4.3.2.13 Women that are pregnant

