5.3 Research Procedures: Subjects enrolled in the chronic PT cohorts will be asked to complete four study visits at baseline, 16 weeks, 32 weeks, and 52 weeks. Subjects enrolled in the control cohort will complete 1 study visit. Health questionnaires (VISA-P Tegner, medication log, side effect log) will be mailed to subjects diagnosed with chronic PT only. A table outlining research visits is below. The following research procedures will be administered:

- 5.3.1 Randomization: The 10 healthy/normal subjects will not be randomized and will not receive any injections. The subjects diagnosed with chronic patellar tendonitis will be randomized to one of three study arms. Subjects in Group 1 (PRP) will receive a single US-guided (USG) injection of 5 mL autologous PRP using a 22G, 1.5 inch needle and after 20 needle passes targeting hypoechoic and hyperemic areas within tendon and bone attachment if involved. Subjects in Group 2 (DN) will undergo USG dry needling with 20 passes using a 22G, 1.5 inch needle targeting hypoechoic and hyperemic areas within tendon and bone attachment if involved. Subjects in Group 3 (SH) will undergo a sham control USG dry needling with 20 passes using a 22G, 1.5 inch needle placed in the subcutaneous tissue only (not intratendon) at the level of the patella tendon.
- 5.3.2 PRP Preparation and Administration (randomized subjects only): At the injection session, a nurse will perform a standard antecubital blood draw (15mL) using a 15 mL syringe and an 18G needle from the PRP group at the contralateral arm. The blood draw will occur only once. The study coordinator will then place the sample in the Arthrex ACP System and spin the blood sample using a two-stage spinning: the 1st separates red blood cells from platelets, and the 2nd concentrates the platelets to yield approximately 6mL of concentrated, autologous platelets. This layer of platelet rich plasma will be placed in the syringe by the centrifuge machine. Centrifuging will be repeated if desired concentration level is not achieved, but this has not occurred clinically and we do not anticipate inadequate platelet concentration level. All blood and equipment handling will follow universal precautions.

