5.3.6 US Protocol: All subjects will undergo an US examination of the patellar tendon using both LOGIQ E9 (GE Healthcare Waukesha, WI) and Aixplorer (Supersonic Imagine, Aix-en-Provence, France) imaging systems with a 15-6MHz linear array transducer. Use of two US imaging systems will allow comparison of SWS measurements across different vendor platforms, which would be important for repeatability in future large-scale clinical trials. Imaging will take approximately 60 minutes total to complete.

5.3.6 Review of Medical Records (All subjects):
The following information will be collected from the randomized subjects: Patient age, height, weight, history of PT pain, duration of symptom related to PT, past medical history, past surgical history, medication history and current use, medication allergy.
The following information will be collected from the healthy/normal subjects: Patient name, height and weight, phone number, lifestyle and health history.

*Randomized subjects only

Procedure	Measurements	Assessment Time (weeks)			
		0	16*	32*	52*
Signed Consent and Randomization		✓			
PRP Procedure*	Collection, processing and administration	✓			
VISA-P Tegner*	Pain and function score of PT	✓	✓	✓	✓
Symptoms/Biomechanics	Knee Strength testing	✓	✓		✓
MRI	Single/bi-component UTE-T2*, PT volume	✓	✓		✓
Conventional US	PT thickness, echogenicity, hyperemia	✓	✓		✓
SWI	SWS measurements	✓	✓		✓
Medication/PT Log*	Pain medicine use, eccentric exercise adherence	✓	✓	✓	✓
Side Effects Log*	Side effects	✓	✓	✓	✓
Exit Interview	Satisfaction score, qualitative assessment of study experience				✓

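### Section 8.0 plans VISA-P on unadjusted change and names no baseline covariate, although baseline VISA-P is already collected

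*Combined protocol and SAP*

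**What the plan says.** Section 8.0 lists hypothesised mean changes in VISA-P by arm (5.5 for DN and for SH; 11, 16.5 or 22 for PRP). Table 2 gives power at 20 per group from these changes together with "the pooled SD of the changes in VISA-P scores". The section names no test, model, covariate or primary time point, and no other section supplies them.

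Baseline VISA-P will be available. The section 5.3 schedule ticks the VISA-P and Tegner row ("Pain and function score of PT") at weeks 0, 16, 32 and 52 for randomised subjects. Aim 3.1.1 also lists VISA-P with "Tegner activity level scores, and knee strength at baseline, 16, 32, and 52 weeks post-treatment".

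On allocation, section 5.3.1 says "The subjects diagnosed with chronic patellar tendonitis will be randomized to one of three study arms" and describes no stratification by baseline severity.

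**The concern.** The only analysis that section 8.0 implies is a comparison of raw change between arms. Subtracting baseline fixes its coefficient at 1, whereas ANCOVA estimates the coefficient from the data and so uses the same measurement more efficiently in most settings. With 20 evaluable patients per arm, precision is scarce. The text expects PRP to improve about three times as much as the other arms, which is the 16.5-point row of Table 2. At the source study's SD of change, stated "to be between 15 and 19 and the minimal detectable" change, unadjusted power for that row recomputes to about 64% at SD 15 and 44% at SD 19.

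There is also a prespecification issue. If the plan is silent, the choice between a change score and an adjusted analysis can be made after the data are seen, and with arms this small the two can give different answers.

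**Working it through.** **Inputs from section 8.0:** 20 evaluable per arm, three arms, the changes listed above, and SD of change 5 to 20. **Assumed, because the documents do not give them:** alpha 0.05; the correlation rho between baseline and week-52 VISA-P; the baseline SD s0 and follow-up SD s1.

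**Step 1: reproduce Table 2.** One-way three-group ANOVA on change, noncentral F with 2 and 57 df, lambda = 20 × Σ(change − mean)² / SD². For PRP 22 the mean is 11 and the sum of squares is 30.25 + 30.25 + 121 = 181.5, so at SD 20 lambda = 20 × 181.5 / 400 = 9.075.

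| PRP change | SD | lambda | Recomputed power (%) | Printed (%) |
|---|---|---|---|---|
| 22 | 10 | 36.30 | 99.98 | 99.9 |
| 22 | 15 | 16.13 | 94.8 | 94.8 |
| 22 | 20 | 9.08 | 75.1 | 75.1 |
| 16.5 | 10 | 16.13 | 94.8 | 94.8 |
| 16.5 | 20 | 4.03 | 39.9 | 64.2 |
| 11 | 5 | 16.13 | 94.8 | 94.8 |

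Five of six rows match to within 0.1 point, so the table rests on unadjusted change. The fifth row does not match: 64.2% is the value at SD 15. That is a separate error.

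**Step 2: compare the variances.**

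- Var(change) = s0² + s1² − 2·rho·s0·s1
- Var(ANCOVA residual) = s1²(1 − rho²)
- Difference = (s0 − rho·s1)², which is never negative

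With k = s0/s1, the ratio of ANCOVA to change variance is (1 − rho²)/(k² + 1 − 2·rho·k). For k = 1 this is (1 + rho)/2.

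**Step 3: estimation cost.** One error df (57 to 56) costs at most about 0.04 points of power. Chance imbalance in the covariate inflates the variance by 1 + 1/(60 − 3 − 2) = 1.018 on average.

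**Step 4: power for the three-group test,** with lambda divided by the variance ratio and 56 error df. The figure in brackets also includes the factor 1.018.

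| k | rho | Variance ratio | PRP 22, SD 20 (75.1% unadjusted) | PRP 16.5, SD 20 (39.9% unadjusted) |
|---|---|---|---|---|
| 1 | 0.3 | 0.65 | 91.3 (90.8) | 57.5 (56.7) |
| 1 | 0.5 | 0.75 | 86.8 (86.1) | 51.2 (50.4) |
| 1 | 0.7 | 0.85 | 82.0 (81.3) | 46.0 (45.3) |
| 1 | 0.9 | 0.95 | 77.3 (76.5) | 41.8 (41.1) |
| 0.7 | 0.3 | 0.85 | 82.0 (81.3) | 46.0 (45.3) |
| 0.7 | 0.5 | 0.95 | 77.3 (76.6) | 41.8 (41.1) |
| 0.7 | 0.7 | 1.00 | 75.0 (74.2) | 39.9 (39.3) |
| 0.7 | 0.9 | 0.83 | 83.1 (82.4) | 47.2 (46.4) |

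The k = 0.7 rows are included because the entry criteria in section 4.3.1, such as "Pain score of 3 or greater on a 10-point VAS" and failed prior treatment, may narrow the spread of baseline scores. The gain is smallest where rho equals k, and it rises again beyond that.

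Simulation of 20,000 trials per scenario (PRP 22, SD 20, k = 1) gave 91.1, 86.0, 81.4 and 76.5% for ANCOVA against 75% for change. In the nil-gain case (k = 0.7, rho 0.7) it gave 74.2% against 74.9%. The bracketed figures are therefore the ones to rely on.

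**Step 5: what a chance imbalance does to the raw contrast.** With k = 1, s = SD of change / √(2(1 − rho)), the SE of the baseline difference between two arms of 20 is s√(2/20), and the shift from a one-SE imbalance is (1 − rho) × SE. At rho 0.5, s equals the SD of change. For SD 15 to 20 the SE is then 4.7 to 6.3 and the shift is 2.4 to 3.2 points. The planned difference is 16.5 − 5.5 = 11 points. At rho 0.3, 0.7 and 0.9 the shift is 2.8–3.7, 1.8–2.4 and 1.1–1.4 points.

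**The case against.** The strongest reply is that section 8.0 is a sample-size paragraph. It commits to no analysis, and basing power on the SD of change is ordinary practice even when ANCOVA will be run. On this view the real defect is that no primary model is specified, and the covariate is one clause of that remedy. It is true that the plan makes no commitment. But the only comparison it describes is an unadjusted one, and a specific, better alternative can be named now from data already scheduled.

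Second, the size of the gain is unknown, since rho and the SDs are not in the documents, and it runs from nil to about 16 points for the PRP 22, SD 20 row. This stands, and it is why the results are shown as scenarios. The balance still favours adjustment, because the worst loss is under one point.

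Third, both analyses are unbiased under randomisation and control type I error, and the shift in step 5 is already contained in the SE of the change contrast. This also stands. The shift shows the same loss of precision from another side: it is error conditional on an observed imbalance, not bias on average, and should not be counted as a second harm.

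Fourth, the cost of one df applies to a single time point. A repeated-measures model with baseline-by-visit terms uses a few more. That is correct and does not change the conclusion.

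**Conclusion.** The concern holds. Section 8.0 bases VISA-P on unadjusted change and names no baseline adjustment, although week-0 VISA-P is scheduled for every randomised patient. Under a three-group F test with 20 per arm, alpha 0.05 and equal SDs, adjustment raises power for PRP 22 and SD 20 from 75.1% to between 76.5% (rho 0.9) and 90.8% (rho 0.3), net of the estimation cost. With a narrower baseline spread the gain may vanish, for a loss of less than one point. Precision therefore usually improves, but not always, and the amount for this trial cannot be fixed from the documents. Validity is not in question. The change is worth making because it needs nothing the trial does not already collect and it closes a choice that should not be left until after the data are seen.

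**What to change.** In section 8.0, state that VISA-P is compared between arms with baseline VISA-P as a covariate, either by ANCOVA at week 52 or by a repeated-measures model over weeks 16, 32 and 52 with the week-52 contrast primary. Week 52 matches the one-year horizon of the section's own hypothesis. State also that the Tegner, strength and imaging outcomes are each adjusted for their own week-0 value, which the schedule already collects.

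Table 2 can stay on unadjusted change if it is labelled as the conservative basis, with its fifth row reconciled separately.

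The cost is a few sentences in section 8.0, about one degree of freedom for the single-time-point analysis and about 2% variance inflation at 60 patients. No new patients, visits or data are needed.

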1.0 PROJECT SUMMARY

BACKGROUND AND RATIONALE

Patellar tendinopathy (PT) is a common disabling overuse injury that is highly prevalent in sports, especially amongst jumping athletes. PT affects 32% of elite basketball players and may lead to considerable long-term morbidity, resulting in a negative effect on their career with up to 50% of athletes forced to quit their sport. Treatment of PT remains challenging, and no currently available conservative therapies directly address the underlying pathophysiology of tissue degeneration. We will conduct a 52-week double-blinded randomized controlled clinical study to investigate the efficacy of PRP and to determine if the intervention truly provides better improvements in pain and function and enhanced tissue healing when compared to less expensive minimally-invasive treatment options.

OBJECTIVES

The overall goal of this proposal is to find an effective treatment for PT. To achieve this, we will conduct a double-blinded randomized controlled trial (RCT) to investigate if platelet-rich plasma (PRP) is effective for treating PT (4-6). Clinical (pain and function scores) and biomechanical (knee strength) measures will be correlated with disease modification changes assessed using conventional and novel quantitative magnetic resonance imaging (MRI) and ultrasound (US) techniques.

ELIGIBILITY

This research will target adults, ages 18 to 39 years, diagnosed with chronic (>3 months) patellar tendonitis. Diagnosis will require a clinical examination consistent with PT and/or MRI or ultrasound confirmation of PT. In addition, 10 healthy/normal subjects who are not diagnosed with chronic PT will be enrolled into a control cohort.

STUDY DESIGN

Sixty-six patients with PT will be randomized to one of three study arms. Subjects in Group 1 (PRP) will receive a single US-guided (USG) injection of 5 mL autologous PRP into the patellar tendon, subjects in Group 2 (DN) will undergo USG dry needling of the patellar tendon, and subjects in Group 3 (SH) will undergo a sham control USG dry needling in the subcutaneous tissue only (not intratendon) at the level of the patellar tendon. The efficacy of the different treatment options will be assessed by pain- and function-dependent, PT-specific Victorian Institute of Sport Assessment Patella (VISA-P) quality of life scores, Tegner activity level scores, knee strength measurements, and conventional and novel MRI and US imaging at baseline, 16, 32, and 52 weeks post-treatment.

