Ten subjects without PT will comprise the healthy/normal or control cohort. The control subjects will undergo the clinical and biomechanical assessments and conventional and novel MRI and US imaging during a single study visit.

REQUIRED SAMPLE SIZE

With 20 subjects, the expected power of our study based on hypothesized changes over time and the pooled SD of the changes in VISA-P scores. To allow for 10% drop out, we will recruit 22 subjects per group. Based on the estimated SD for the changes in the VISA-P scores reported in the previous study, we are conservatively inflating our pooled SD estimate. The data collected from the 10 control subjects will be used to compare normative data to the data collected from the test population.

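### Table 2 does not support the claim of a conservatively inflated SD for the hypothesised 3-fold effect: power is 64% to 44% over the cited SD range and about 40% at SD 20

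*Combined protocol and SAP*

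**What the plan says.** Section 8.0 (Statistical Considerations) relies on an earlier study that "estimated the pooled standard deviation (SD) of the changes in VISA-P score over time to be between 15 and 19". It expects the dry-needling (DN) and sham (SH) arms to change little and hypothesises that the "PRP group will significantly improve on the order of 3 times the improvement of the other groups". It then says "table 2 shows the expected power of our study based on hypothesized changes over time and the pooled SD" and closes with the statement that "we are conservatively inflating our pooled SD estimate". No value is given for the inflated SD, and no test, alpha or target power is stated.

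Table 2 has six rows, all with 20 per group and a change of 5.5 in both DN and SH:

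- PRP change 22 at SD 10, 15 and 20: power 99.9%, 94.8% and 75.1%.
- PRP change 16.5 at SD 10 and 20: power 94.8% and 64.2%.
- PRP change 11 at SD 5: power 94.8%.

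No row is named as the design case. The Required Sample Size paragraph of Section 1.0 repeats the inflation sentence but gives neither the SD range nor a power figure.

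**The concern.** With 5.5 in the comparison arms, three times is 16.5, so rows 4 and 5 are the trial's own hypothesis. Row 4 uses SD 10, well below the cited 15 to 19. Row 5 uses SD 20, above that range, but its power looks too high beside the other rows. The rows at SD 15 and SD 20 with the more reassuring figures (94.8% and 75.1%) assume a PRP change of 22, which is 4-fold.

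At stake is what 66 randomised patients can show. A reader takes from the table that power for the hypothesised effect lies between 64.2% and 94.8%, with the lower figure already allowing for a pessimistic SD. If the true figures are lower, a null result could be read as evidence against PRP when the trial had a large chance of missing the effect it was planned to find.

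**Working it through.** **Inputs.** n = 20 per group, three groups, DN and SH change 5.5, PRP change 22, 16.5 or 11, and SDs as printed (Section 8.0, Table 2). Cited SD range 15 to 19 (Section 8.0). Assumption: overall one-way F test at alpha 0.05, because the documents name neither and this choice reproduces five of the six rows.

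**Formula.** Noncentrality λ = n·Σ(μᵢ − mean)²/SD², with 2 and 3(n − 1) = 57 degrees of freedom. Power is the probability that the noncentral F exceeds the central 95% point, 3.159. For two arms at 5.5 and PRP higher by d, Σ(μᵢ − mean)² = (2/3)d². This is 181.5 for d = 16.5, 80.67 for d = 11 and 20.17 for d = 5.5.

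**Reproducing Table 2.**

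| Row | PRP change | SD | d/SD | λ | Printed % | Computed % |
|---|---|---|---|---|---|---|
| 1 | 22 | 10 | 1.65 | 36.30 | 99.9 | 99.98 |
| 2 | 22 | 15 | 1.10 | 16.13 | 94.8 | 94.8 |
| 3 | 22 | 20 | 0.825 | 9.08 | 75.1 | 75.1 |
| 4 | 16.5 | 10 | 1.10 | 16.13 | 94.8 | 94.8 |
| 5 | 16.5 | 20 | 0.55 | 4.03 | 64.2 | **39.9** |
| 6 | 11 | 5 | 1.10 | 16.13 | 94.8 | 94.8 |

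Row 5 is about 24 points too high. Solving for the SD that gives 64.2% with d = 11 returns 15.00 (d/SD = 0.733). To reach 64.2% at SD 20 would take about 35 per group (34 gives 63.2%, 35 gives 64.6%) or a PRP change of 20.2.

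**A check inside the table.** At fixed n and a given test, power depends only on d/SD. Rows 2, 4 and 6 share 1.10 and all print 94.8%. From 0.825 to 1.10 the printed power rises by 94.8 − 75.1 = 19.7 points. From 0.55 to 0.825, the same step of 0.275, it rises by only 75.1 − 64.2 = 10.9. A power curve flattens as it nears 100%, so the lower step should be the larger one. The computed step is 75.1 − 39.9 = 35.2.

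**Other tests.** Each was compared with printed rows 2, 3 and 5 (94.8, 75.1, 64.2):

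- PRP vs pooled DN and SH, two-sided 0.05 (SE = SD·√(1.5/20), 57 df): 97.7, 84.2, 50.6.
- The same contrast, one-sided 0.05: 99.0, 90.8, 63.3.
- PRP vs one arm, two-sided 0.05 (SE = SD·√(2/20), 38 df): 92.4, 72.0, 39.6.

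The one-sided contrast comes close on row 5 but misses row 3 by almost 16 points. None reproduces the table.

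**Power for the 3-fold effect (5.5/5.5/16.5).**

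| Test | SD 15 | SD 17 | SD 19 | SD 20 |
|---|---|---|---|---|
| F test, n = 20 | 64.2 | 52.8 | 43.7 | 39.9 |
| F test, all 22 retained | 68.9 | 57.3 | 47.7 | 43.6 |
| PRP vs pooled, two-sided, n = 20 | 74.9 | 64.2 | 54.7 | 50.6 |
| PRP vs pooled, one-sided, n = 20 | 84.2 | 75.5 | 67.1 | 63.3 |
| PRP vs one arm, two-sided, n = 20 | 61.8 | 51.4 | 43.0 | 39.6 |

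For a 2-fold effect (PRP change 11), which the table shows only at SD 5, the F test gives 19.7, 16.2, 13.8 and 12.9% at the same SDs.

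**The case against.** The strongest reply is that row 5 is a simple misprint of 20 for 15. The row would then be correctly computed, and the 3-fold effect would appear inside the cited range. The documents cannot exclude this, and the exact match at SD 15 makes it plausible. But it does not rescue the inflation claim: 15 is the bottom of the cited range, so no inflated SD would then be shown for the 3-fold effect.

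Second, the table does contain a correctly computed SD above the range (row 3, SD 20, 75.1%). The hypothesis is also worded approximately, and the table brackets it with PRP changes of 11, 16.5 and 22. That is true, but row 3 assumes a 4-fold effect. The 2-fold effect on the other side is shown only at SD 5, so the bracketing is not done at comparable SDs.

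Third, the power figures are conditional. Neither test nor alpha is stated, VISA-P is collected at four time points, and a baseline-adjusted or repeated-measures analysis could have different power. This stands: the figures describe the test that Table 2 evidently used, not necessarily the eventual analysis.

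Fourth, the protocol sets no target power, so 80% is an outside convention. This also stands, and the comparison depends on the test. Power of 80% for the 3-fold effect needs an SD of at most 12.6 (F test) or 14.1 (two-sided pooled contrast), while the one-sided pooled contrast exceeds 80% at SD 15.

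**Conclusion.** The concern holds. Row 5's SD and power are incompatible under the only test examined that fits the other rows, and either correction leaves the 3-fold effect without a correctly computed figure at an inflated SD. If the power is the error, the printed value overstates it by 24 points (64.2% against 39.9%). If the SD is the error, the least favourable figure shown for the hypothesis is at the low end of the cited range.

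On the assumed F test at 0.05 with 20 per group, the chance of missing the hypothesised effect is about 36% to 56% over SD 15 to 19 and about 60% at SD 20. The finding rests on that inferred test and on reading 16.5 as the 3-fold case. The row 5 mismatch needs only the first of these.

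**What to change.** No change in sample size is needed.

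1. State the test and alpha behind Table 2.
2. Report the 3-fold effect (5.5/5.5/16.5) at SD 15, 17, 19 and 20 as the main scenario: 64.2, 52.8, 43.7 and 39.9% under the F test at 0.05, recomputed if another test is chosen.
3. Correct row 5 in the same edit: either SD 15 with 64.2%, or SD 20 with 39.9%.
4. Label the SD 5 and SD 10 rows as below the cited range, and the PRP 22 rows as a 4-fold effect.
5. In Sections 1.0 and 8.0, either name the inflated SD and its power for the 3-fold effect (20 is the only tabulated value above the range) or delete the inflation sentence.

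The cost is one table and wording in two places. The drawback is a visibly lower stated power for the hypothesised effect, roughly 40% to 64% where the table now prints 64.2% and 94.8%, which the sponsor may have to justify.

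### Section 8.0 calls its VISA-P SD conservatively inflated, yet half of Table 2 uses SDs below the cited 15–19; the stated 3-times effect is never shown at a cited SD, where power is about 44–64%

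*Combined protocol and SAP*

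**What the plan says.** Section 8.0 is the only sample-size justification. It makes three statements that have to fit together.

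- **Variability.** A similar study "estimated the pooled standard deviation (SD) of the changes in VISA-P score over time to be between 15 and 19".
- **Treatment of that figure.** "we are conservatively inflating our pooled SD estimate". The same sentence appears in section 1.0 under Required Sample Size, without any figures.
- **Effect.** The DN and SH arms are expected to improve marginally, and "the PRP group will significantly improve on the order of 3 times the improvement of the other groups" over one year.

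Table 2 then gives power for 20 per arm. In column order (n, DN, SH, PRP, SD, power), the first five rows are:

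- Row 1: "20 5.5 5.5 22 10 99.9"
- Row 2: "20 5.5 5.5 22 15 94.8"
- Row 3: "20 5.5 5.5 22 20 75.1"
- Row 4: "20 5.5 5.5 16.5 10 94.8"
- Row 5: "20 5.5 5.5 16.5 20 64.2"

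Row 6 has PRP at 11 and SD 5, with 94.8%. No row is named as the design basis, and neither the test nor alpha is stated. Recruitment is 22 per arm, to allow for 10% dropout.

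**The concern.** An inflated SD should lie at or above the top of the evidence. Table 2 uses SDs of 10, 15, 20, 10, 20 and 5. Rows 1, 4 and 6 lie below the cited range, row 2 is at its floor, and only rows 3 and 5 are above it, by one point over 19.

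The effect sizes add to the difficulty. Rows 1–3 set PRP at 22, which is four times 5.5. Row 6 is a 2-times case. Only rows 4 and 5 carry the stated 3-times effect, one at SD 10 and the other at SD 20. A reader therefore cannot find the plan's own hypothesis at the plan's own SD. The only 3-times row at or above 80% depends on an SD that the cited study does not support.

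At stake is how 20 completers per arm is understood: as a design with a margin on variability, or as one with roughly even odds of detecting the effect it hypothesises.

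**Working it through.** **Inputs (section 8.0 and Table 2).** n = 20 per arm, three arms; DN and SH change 5.5; PRP change 22 (4 times), 16.5 (3 times) or 11 (2 times); cited SD 15–19. Assumed, because it is not stated: a one-way three-group F test at alpha 0.05.

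**Formula.** Power is the probability that a noncentral F with 2 and 57 degrees of freedom exceeds the 5% critical value, 3.159. The noncentrality is λ = n·Σ(μᵢ − μ̄)²/SD². With two equal arms and one that differs by d, the sum is (2/3)d², so λ = 20 × (2/3) × d²/SD². Power therefore depends only on d/SD.

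**Reproducing Table 2.**

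| Row | d | SD | d/SD | λ | Power, F test | Printed |
|---|---|---|---|---|---|---|
| 1 | 16.5 | 10 | 1.65 | 36.30 | 99.98% | 99.9 |
| 2 | 16.5 | 15 | 1.10 | 16.13 | 94.8% | 94.8 |
| 3 | 16.5 | 20 | 0.825 | 9.08 | 75.1% | 75.1 |
| 4 | 11 | 10 | 1.10 | 16.13 | 94.8% | 94.8 |
| 5 | 11 | 20 | 0.55 | 4.03 | **39.9%** | **64.2** |
| 6 | 5.5 | 5 | 1.10 | 16.13 | 94.8% | 94.8 |

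Row 1 agrees if its figure was cut rather than rounded; rows 2, 3, 4 and 6 agree to the decimal. Rows 2, 4 and 6 share d/SD = 1.10, which is why they share 94.8%.

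Row 5 does not reproduce. The F test gives 64.2% at SD 15, so either the SD or the power in that row is wrong. Other methods do not rescue it. At SD 20, a two-sided pairwise t test gives 39.6%, a one-sided one 52.5%, and the F test at alpha 0.10 gives 53.1%. A one-sided contrast of PRP against the other two arms comes close to row 5 (63.3%), but then gives 90.9% for row 3, printed as 75.1%.

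**The 3-times effect (d = 11) at the cited SDs, n = 20.**

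| SD | λ | Power |
|---|---|---|
| 15 | 7.17 | 64.2% |
| 17 | 5.58 | 52.8% |
| 19 | 4.47 | 43.7% |
| 20 | 4.03 | 39.9% |

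With all 22 per arm retained, power is 68.9% at SD 15 and 47.7% at SD 19.

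**The 4-times effect (d = 16.5), n = 20.** 94.8% at SD 15, 79.6% at SD 19 and 75.1% at SD 20.

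**Difference giving 80% power, n = 20.** 13.1 points at SD 15, 16.6 at SD 19 and 17.5 at SD 20, against the 11 in rows 4 and 5. Conversely, d = 11 reaches 80% only if the SD is about 12.6 or less, below the cited range.

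**Sensitivity to the assumed test.** Two-sided pairwise t tests of PRP against one arm give 61.8% (SD 15) to 43.0% (SD 19). With a Bonferroni correction for two comparisons they give 50.0% to 31.9%. A two-sided contrast of PRP against the other two arms pooled is more favourable, 74.9% to 54.7%. None of these reaches 80%.

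**The case against.** Table 2 can be read as a sensitivity grid, since no row is called the design basis. On that reading, optimistic rows beside pessimistic ones are not an error. SD 20 exceeds the whole cited range and is about 18% above its midpoint of 17 (20/17 = 1.18), and the documents set no threshold for calling an SD conservative. The effect is worded as an order of magnitude, so the 4-times rows are a near alternative, with 79.6% to 94.8% power across SD 15–19.

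Much of this stands. In particular, a reader might infer that the plan presents its 3-times hypothesis as 94.8% powered. The documents do not support that. The same hypothesis is printed again in row 5, at an SD that is inflated, with 64.2%. The plan thus already shows power below 80% for its hypothesis, although that figure is itself too high. Nor can one say that no inflation occurs, since rows 3 and 5 apply it. A reader might also infer that a null result will be over-interpreted; the documents do not say how one would be read.

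What does not stand is the grid as support for the sentence about inflation. A grid in which half the rows lie below the cited range does not show a conservative SD, and this grid omits the stated effect at the cited SDs. If row 5's SD is the misprint and should be 15, the 3-times case would appear only at the floor of the range and at SD 10, with no inflated SD at all.

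**Conclusion.** The point holds. The description of the SD does not match Table 2: three of six rows use 5 or 10 against a cited 15–19, and two exceed 19. The stated hypothesis is not shown at any SD in the cited range, where its power with 20 per arm runs from 64.2% down to 43.7%. At SD 20 it is 39.9%, so row 5 as printed overstates power by about 24 percentage points (64.2 − 39.9 = 24.3).

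These figures rest on a three-group F test at alpha 0.05, inferred because it reproduces five of six rows, and on reading the 3-times hypothesis as 16.5 against 5.5, as rows 4 and 5 do. The conclusion that power is below 80% throughout the cited range does not depend on choosing the F test over the two-sided alternatives tried. The finding concerns how the sample size is justified; it does not show that the planned enrolment must change.

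**What to change.** In section 8.0:

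1. State the test and alpha behind Table 2.
2. Restate the table for the 3-times and 4-times cases at SD 15, 19 and a value of 20 or more.
3. Correct row 5: either the SD is 20 and the power 39.9%, or the power is 64.2% and the SD 15.
4. Name the row that is the design basis.
5. Remove the SD 5 and SD 10 rows, or label them as optimistic sensitivity cases below the cited range.
6. Delete the claim of conservative inflation unless the design row uses an SD above 19.

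In sections 8.0 and 1.0, state that 20 completers per arm give about 40–64% power for the 3-times hypothesis (SD 20 down to 15), and 80% only for differences of about 13 to 17.5 points. If the stated test is not the F test, recompute these figures for it. Make the wording change in both sections.

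The cost is one table and a few sentences. Enrolment and conduct are unaffected; the stated power becomes less favourable.
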